4.6.5.5.4. Analyses to be Performed

The count and proportion of participants who are TE ADA+ will be tabulated by treatment group, where proportions are relative to the number of participants who are TE ADA evaluable, as defined above. The tabulation will include the number and proportion of participants with

ADA Present at baseline and the number and proportion of TE-ADA+ participants exhibiting each type of cross-reactive antibody and NAb. This analysis will be performed for the following periods:

- the planned treatment period, and
- the entire postbaseline period, including safety follow-up.

The *in silico* classification for cross-reactive NAb will be summarized.

A summary will be provided of the count and percentage of tirzepatide-treated participants experiencing a specific TEAE (see [Table GPHM.4.10](#)) by participant TE-ADA status (TE ADA+, TE ADA-, or TE ADA Inconclusive).

Table GPHM.4.10. Adverse Events for Analysis with Immunogenicity Results

TEAE Category	Criteria
Hypersensitivity reactions	Anaphylaxis SMQ (narrow or algorithm)
	Hypersensitivity SMQ (narrow)
	Angioedema SMQ (narrow)
	Severe Cutaneous Adverse Reaction SMQ (narrow)
	Vasculitis SMQ (narrow)
Injection site reactions	Injection site reaction HLT
	Infusion site reaction HLT
	Administration site reaction HLT

Abbreviations: HLT = High-Level Term; MedDRA = Medical Dictionary for Regulatory Activities; SMQ = Standardized MedDRA Query; TEAE = treatment-emergent adverse event.

A listing will be provided for all participants who had ADA Present at any time (including baseline) or had any specific TEAE (see [Table GPHM.4.10](#)). This listing includes a time course of ADA (clinical interpretation result plus flags for samples meeting TE ADA+ criteria and for samples with cross-reactive antibodies and NAb present) along with the TEAE.

Cases of TE ADA that are associated with AEs of either severe/serious hypersensitivity or severe/serious injection site reaction (ISR) will be classified as AESI.

Additional immunogenicity analyses, as determined later, may be presented. The relationship between antibody titers, the PK parameters, and pharmacodynamic (PD) response to tirzepatide may also be assessed.

4.6.5.6. Hypersensitivity Reactions

Two main analyses are performed in support of assessment of potential immediate hypersensitivity, including anaphylaxis, as well as potential nonimmediate hypersensitivity.

Time Period A of potential immediate hypersensitivity includes all TEAEs occurring from start of study drug administration up to 24 hours after end of study drug administration. For events without the hypersensitivity eCRF, only date (no time) information is collected. If such events occurred on the same date as the study drug injection date, they will be included in Time Period A.

Time Period B of potential nonimmediate hypersensitivity includes all TEAEs occurring more than 24 hours after the end of study drug administration but prior to subsequent drug administration.

The counts and percentages of participants who experienced a hypersensitivity TEAE will be summarized by PT with decreasing frequency by treatment.

Analyses for both time periods are based on the following:

- narrow and algorithm terms in the Anaphylactic reaction Standardized MedDRA Query (SMQ) (20000021) (note that the Anaphylactic reaction SMQ algorithm will only be summarized for Time Period A)
- narrow terms in the Angioedema SMQ (20000024)
- narrow terms in the Severe cutaneous adverse reactions SMQ (20000020)
- narrow terms in the Hypersensitivity SMQ (20000214), and
- narrow terms in the Vasculitis SMQ (20000174).

For the Anaphylactic reaction SMQ, each term is classified by scope (narrow, broad) and by category (A, B, C, D). All narrow terms are Category A, and all broad terms are Category B, C, or D. In addition to the usual narrow and broad searches, the SMQ defines an algorithm to further refine the cases of interest. For Time Period A analysis, the Anaphylactic reaction SMQ algorithm will be included. The algorithm is based upon events that occur within Time Period A.

The counts and percentages of participants who experienced a TEAE for the following will be analyzed for each of the 2 time periods:

- any narrow term from any one of the 5 SMQs indicated above (that is, combined search across the narrow scope of all 5 SMQs), and
- any narrow term within each SMQ, separately (that is, narrow SMQ search)
 - for Time Period A analysis, any term from the Anaphylactic reaction SMQ algorithm.

Within queries, individual PTs that satisfied the queries will be summarized. For Time Period A analysis, the Anaphylactic reaction SMQ algorithm will be summarized. Also, a single event may satisfy multiple SMQs, in which case, the event contributes to every applicable SMQ.

4.6.5.6.1. *Serious Hypersensitivity Reactions*

The severe/serious cases of hypersensitivity will be considered AESI. A summary with severe/serious hypersensitivity reactions may be provided, if deemed necessary.

4.6.5.7. *Injection Site Reaction*

Injection site reactions, incidence and rates, and related information reported via the “Injection Site Reactions” eCRF will be summarized by treatment. Information to be summarized includes the location of the reaction, timing of the reaction relative to study drug administration, and characteristics of the ISR: erythema, induration, pain, pruritis, and edema.

Patient-based analysis and event-based analysis may be provided if necessary. The patient-based analysis summarizes all ISR questionnaire forms for an individual participant with a single statistic, typically an extreme value. This analysis allows each participant to contribute only once for each parameter, at the expense of a focus on the most extreme events. By contrast, the event-based analysis summarizes all ISR questionnaire forms received, without regard to individual participants. This provides characteristics of ISR events as a proportion of all events for which questionnaire responses were provided, at the expense of some potential bias due to differential contribution of individual participants to the analysis.

The counts and percentages of participants with treatment-emergent ISRs will be summarized by treatment using MedDRA PTs. Detailed searching criteria can be found in Appendix 7 (Section 6.7).

The PT will be summarized in decreasing order of incidence for tirzepatide-treated participants.

4.6.5.7.1. Severe/Serious Injection Site Reactions

The severe/serious treatment-emergent ISRs, based on the TEAE search criteria specified in Appendix 6.7 (Section 6.7), will be considered AESI. The counts and percentages of participants with severe/serious ISRs will be summarized by treatment. A listing of participants with treatment-emergent severe/serious ISRs may be provided, if deemed necessary.

4.6.5.8. Major Adverse Cardiovascular Events

The following positively adjudicated major adverse cardiovascular events (MACE) will be considered AESI:

- death due to cardiovascular AEs
- myocardial infarction
- hospitalization for unstable angina
- hospitalization for heart failure
- coronary interventions (such as coronary artery bypass graft or percutaneous coronary intervention), and
- cerebrovascular events, including cerebrovascular accident (stroke) and transient ischemic attack.

The counts and percentages of participants with positively adjudicated MACE may be summarized by treatment.

A listing of participants reporting MACE events, either reported by the investigator or identified by the CEC, may be provided.

In addition, MACE reported by the investigator may be summarized, although a MACE reported by the investigator and not positively adjudicated is not considered an AESI.

4.6.5.9. Major Depressive Disorder/Suicidal Ideation

The severe/serious major depressive disorder/suicidal ideation or behavior will be captured as AESI. Adverse events will be searched using MedDRA PTs. Detailed searching criteria can be found in Appendix 7 (Section 6.7).

The counts and percentages of participants with TEAEs will be summarized by treatment group using MedDRA PT nested within SMQ. Events will be ordered by decreasing frequency nested within SMQ. A listing of participants with major depressive disorder/suicidal ideation or behavior may be provided if deemed necessary.

In addition to spontaneously reported AEs assessed by the investigator, suicidal ideation and behavior and depression will be assessed through the use of the Columbia-Suicide Severity Rating Scale (C-SSRS) and the Patient Health Questionnaire (PHQ-9), respectively.

4.6.5.9.1. Patient Health Questionnaire

Total scores for the PHQ-9 range from 0 to 27 with total scores being categorized as follows:

- None (not depressed) - 0 to 4.
- Mild - 5 to 9.
- Moderate - 10 to 14.
- Moderately Severe - 15 to 19.
- Severe - 20 to 27.

Shift tables will be provided showing the counts and percentages of participants within each baseline category (maximum value) versus each postbaseline category (maximum value) by treatment.

Additionally, the following 3 outcomes of interest will be compared between treatments (based on the maximum value during baseline and postbaseline):

- Any increase in depression category (that is, worsening of depression) - Includes participants in the none, mild, moderate, or moderately severe categories during baseline with at least 1 postbaseline measurement.
- Increase from no or mild depression to moderate, moderately severe or Severe depression - Includes participants in the none or mild depression category during baseline with at least 1 postbaseline measurement.
- Increase from mild or moderate depression to moderately severe or severe depression - includes participants in the mild or moderate depression category during baseline and at least 1 postbaseline measurement.

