#### *Other Medical*

11. Have renal impairment measured as estimated glomerular filtration rate (eGFR)  $<30$  mL/min/1.73 m^2, calculated by Chronic Kidney Disease-Epidemiology (CKD-EPI) as determined by central laboratory during screening
12. Have a known clinically significant gastric emptying abnormality (for example, severe gastroparesis or gastric outlet obstruction) or chronically take drugs that directly affect GI motility
13. Have a history of chronic or acute pancreatitis
14. Have thyroid-stimulating hormone (TSH) outside of the range of 0.4-6.0 mIU/L at the screening visit

**Note:** Participants receiving treatment for hypothyroidism may be included, provided their thyroid hormone replacement dose has been stable for at least 3 months and their TSH at screening falls within the range indicated above.

**Note:** Participants with a history of subclinical hypothyroidism but a TSH at screening within the range indicated above, may be included if in the investigator's opinion, the patient is unlikely to require initiation of thyroid hormone replacement during the course of the study.

15. Have obesity induced by other endocrinologic disorders (for example, Cushing syndrome) or diagnosed monogenetic or syndromic forms of obesity (for example, Melanocortin 4 Receptor deficiency or Prader Willi Syndrome)
16. Have a history of significant active or unstable Major Depressive Disorder (MDD) or other severe psychiatric disorder (for example, schizophrenia, bipolar disorder, or other serious mood or anxiety disorder) within the last 2 years

**Note:** Participants with MDD or generalized anxiety disorder whose disease state is considered stable for the past 2 years and expected to remain stable throughout the course of the study, in the opinion of the investigator, may be considered for inclusion if they are not on excluded medications

17. Have a lifetime history of suicide attempt
18. Have a PHQ-9 score of 15 or more at Visit 1
19. On the C-SSRS at any time from Visit 1 to Visit 2:
  - a "yes" answer to Question 4 (Active Suicidal Ideation with Some Intent to Act, Without Specific Plan) on the "Suicidal Ideation" portion of the C-SSRS
  - or**
  - a "yes" answer to Question 5 (Active Suicidal Ideation with Specific Plan and Intent) on the "Suicidal Ideation" portion of the C-SSRS
  - or**

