### **8.3.2.13. Depression, Suicidal Ideation or Behavior Monitoring**

Participants will be monitored for depression and suicidal ideation or behavior through AE collection and by using the C-SSRS and the PHQ-9. Participants will be referred to an MHP if in the opinion of the investigator it is necessary for the safety of the participant or if the participant had any of the following:

- a PHQ-9 score  $\geq 15$
- C-SSRS responses of
  - A “yes” answer to Question 4 (Active Suicidal Ideation with Some Intent to Act, Without Specific Plan) on the “Suicidal Ideation” portion of the C-SSRS
  - or**
  - A “yes” answer to Question 5 (Active Suicidal Ideation with Specific Plan and Intent) on the “Suicidal Ideation” portion of the C-SSRS
  - or**
  - A “yes” answer to any of the suicide-related behaviors (actual attempt, interrupted attempt, aborted attempt, preparatory act, or behavior) on the “Suicidal Behavior” portion of the C-SSRS

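### The PHQ-9 comparison for reaching 15 or more (SAP 4.6.5.9.1, third outcome) leaves out participants with no depression at baseline, so no planned comparison covers everyone who could newly reach that score

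*SAP*

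**What the plan says.** SAP 4.6.5.9.1 sorts PHQ-9 totals into none (0 to 4), mild (5 to 9), moderate (10 to 14), moderately severe ("Moderately Severe - 15 to 19") and severe (20 to 27). It plans two outputs, both using the maximum value in the baseline and postbaseline periods.

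- A descriptive display by treatment: "Shift tables will be provided showing the counts and percentages of participants within each baseline category", crossed with each postbaseline category.
- Comparisons: "the following 3 outcomes of interest will be compared between treatments". They are:
  1. "Any increase in depression category (that is, worsening of depression) - Includes participants in the none, mild, moderate, or moderately severe categories"
  2. "Increase from no or mild depression to moderate, moderately severe or Severe depression - Includes participants in the none or mild depression category"
  3. "Increase from mild or moderate depression to moderately severe or severe depression - includes participants in the mild or moderate depression category"

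Each outcome also requires at least one postbaseline measurement. SAP 4.6 makes Fisher's exact test the default for categorical safety outcomes.

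The protocol uses the score that starts the moderately severe category in three places. Exclusion criterion 18 in Section 5.2 reads "Have a PHQ-9 score of 15 or more at Visit 1". Section 7.1 lists a score of 15 or more among possible reasons for discontinuation, with referral to a mental health professional to help decide. Section 8.3.2.13, which begins "Participants will be referred to an MHP if in the opinion of the investigator it is necessary for the safety of the participant", lists the same score as a trigger for referral.

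**The concern.** Each outcome asks what share of the participants who could worsen past a given point did so. The natural denominator is everyone who starts below that point. The first outcome follows this rule, since it admits every category that can still rise. The second does too: its event is moderate or worse, and it admits none and mild. The third departs from it. Its event is moderately severe or severe, but it admits mild and moderate and drops none. Neither document gives a reason.

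A participant who goes from 3 at baseline to 18 on treatment is therefore in neither the numerator nor the denominator of the only comparison set at the protocol's own threshold. If a treatment effect appeared mainly as new depression in people without symptoms at entry, the third outcome would not register it, and the first two would show it mixed with smaller rises. Protocol 9.4.4.3 lists major depressive disorder and suicidal behavior and ideation as a topic of special interest. The trial has no data monitoring committee (Protocol 9.6), and the study team's safety review is blinded (8.2.5). The final between-arm analysis therefore carries much of the weight.

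**Working it through.** The plan states no power or sample size figure for the PHQ-9 outcomes, so there is none to reproduce. The check is a count of category shifts, followed by an illustration on assumed rates.

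**Step 1. Which shifts count in which outcome.** Five categories give 5 × 4 / 2 = 10 upward shifts.

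| Baseline to postbaseline | Outcome 1 | Outcome 2 | Outcome 3 | Outcome 3 with none added |
|---|---|---|---|---|
| none to mild | yes | no | no | no |
| none to moderate | yes | yes | no | no |
| none to moderately severe | yes | yes | **no** | **yes** |
| none to severe | yes | yes | **no** | **yes** |
| mild to moderate | yes | yes | no | no |
| mild to moderately severe | yes | yes | yes | yes |
| mild to severe | yes | yes | yes | yes |
| moderate to moderately severe | yes | no | yes | yes |
| moderate to severe | yes | no | yes | yes |
| moderately severe to severe | yes | no | no | no |

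Shifts that cross 15 start in one of three categories (none, mild, moderate) and end in one of two: 3 × 2 = 6. Outcome 3 captures 2 × 2 = 4 of them. The missing two both start from none.

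**Step 2. Where the missing two go.** Both are events in outcomes 1 and 2, and baseline-none participants are in both denominators. Outcome 1 counts them with rises as small as 4 to 5, outcome 2 with rises to 10 to 14. The shift table shows the two cells separately by arm but specifies no comparison.

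**Step 3. Size of the omitted group.** No document gives it. If 50% to 85% of participants scored 0 to 4 at baseline (an assumption), then of 300 per arm 300 × 0.50 = 150 to 300 × 0.85 = 255 fall outside outcome 3. If a further assumed 1% to 2% of them reached 15, that is 150 × 0.01 = 1.5 to 255 × 0.02 = 5.1 cases per arm.

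**Step 4. What pooling does to a signal.** All rates here are assumed and none is in the documents: from none to 15 or more, 1% on placebo and 4% on tirzepatide; from none to moderate, 3% in both arms; from mild or moderate to 15 or more, 5% in both; among those not at none (all treated as mild for outcome 2), 15% to moderate or worse in both. Fisher's exact test, two-sided 0.05, 300 per arm.

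With share s at none, the event rates are:
- widened outcome 3: s × (0.01 or 0.04) + (1 − s) × 0.05;
- outcome 2: s × (0.04 or 0.07) + (1 − s) × 0.15.

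| s | Outcome 3 as written, n per arm | Outcome 2 rates | Power | Widened outcome 3 rates | Power |
|---|---|---|---|---|---|
| 0.5 | 150 | 9.5% v 11.0% | 0.07 | 3.0% v 4.5% | 0.12 |
| 0.7 | 90 | 7.3% v 9.4% | 0.12 | 2.2% v 4.3% | 0.24 |
| 0.9 | 30 | 5.1% v 7.8% | 0.22 | 1.4% v 4.1% | 0.44 |

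Outcome 3 as written carries none of the assumed difference, because its participants have the same rate in both arms. Widening roughly doubles the power of outcome 2 at s = 0.7 and 0.9 and raises it by less at 0.5. Power stays low throughout.

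**The case against.** A reader might infer that new moderately severe or severe depression in people without baseline symptoms is never compared between arms. The documents do not support that. Outcomes 1 and 2 include these participants and count such a rise as an event, and the shift table gives the exact cells by arm with the baseline-none denominator. No data are lost. What is missing is a comparison at 15 that covers everyone below it.

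A reader might also infer that the omitted group is most of the trial. Criteria 16 to 18 make that plausible, but entry allows PHQ-9 scores up to 14 and stable major depression or generalized anxiety disorder may be admitted. Protocol 8.2.6 says people with obesity or overweight are at increased risk of depression. The analysis also uses the maximum baseline value, and PHQ-9 is taken at Visits 1 and 10. If both visits count as baseline, fewer people fall in none than at a single visit.

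The inferential gain is also small. With 150 to 255 per arm, 0 versus 5 cases gives a Fisher p of about 0.06 and 2 versus 5 about 0.45. The widened outcome would still pool baseline none with mild and moderate, so new onset from none alone would remain visible only in the shift table. The adverse event searches (SAP 4.6.5.9) and C-SSRS summaries (4.6.5.9.2) have no PHQ-9 restriction, and referral of individuals does not depend on this analysis.

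All of this stands, and it limits the point to a minor one. It does not explain why one of three parallel outcomes drops an at-risk category, or make the present denominator the right one for its event.

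**Conclusion.** The point holds in a limited form. The third PHQ-9 outcome omits two of the six shifts that cross 15. No planned comparison therefore covers all participants who could newly reach the score on which the protocol itself acts. Those two shifts are compared only in pooled form and are otherwise only tabulated.

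This conclusion needs no assumption beyond there being some participants at 0 to 4 at baseline. The number omitted, the cases involved and the power figures all rest on assumed rates and serve only as illustration. The PHQ-9 outcomes are safety analyses without multiplicity control (SAP 2.1), and the primary and key secondary results are unaffected. It is a cheap improvement worth making.

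**What to change.** In SAP 4.6.5.9.1, redefine the third outcome as a rise to moderately severe or severe depression (PHQ-9 of 15 or more) among all participants whose maximum baseline category is none, mild or moderate and who have a postbaseline score. If consistency with other studies is wanted, keep the present mild-or-moderate version as a labelled subset.

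The cost is one line of SAP text and one changed denominator. The data, the categories and the default Fisher's exact test stay as they are.

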4.6.5.9.2. Suicidal Ideation and Behavior Solicited Through C-SSRS

Suicide-related thoughts and behaviors occurring during the entire study period, based on the C-SSRS, will be summarized by treatment group. In particular, for each of the following suicide-related events, the counts and percentages of participants with the event will be summarized by treatment group:

- died by suicide
- nonfatal suicide attempt
- interrupted attempt
- aborted attempt
- preparatory acts or behavior
- active suicidal ideation with a specific plan and intent
- active suicidal ideation with some intent to act without a specific plan
- active suicidal ideation with any methods (no plan) without an intent to act
- nonspecific active suicidal thoughts
- wish to be dead, and
- nonsuicidal, self-injurious behavior.

In addition, the counts and percentages of participants who experienced at least 1 of the composite measures will be presented. The participants with at least 1 postbaseline C-SSRS assessment are included. The composite measure is determined at each assessment by the “yes” or “no” responses in C-SSRS categories by the study participant:

- Category 1 - Wish to be Dead.
- Category 2 - Non-Specific Active Suicidal Thoughts.
- Category 3 - Active Suicidal Ideation with Any Methods (Not Plan) without Intent to Act.
- Category 4 - Active Suicidal Ideation with Some Intent to Act, without Specific Plan.
- Category 5 - Active Suicidal Ideation with Specific Plan and Intent.
- Category 6 - Preparatory Acts or Behavior.
- Category 7 - Aborted Attempt.
- Category 8 - Interrupted Attempt.
- Category 9 - Actual Attempt (non-fatal).
- Category 10 - Completed Suicide.

Composite endpoints of suicidal ideation and suicidal behavior based on the above categories are defined below:

- **Suicidal ideation** - A “yes” answer at any time during study to any 1 of the 5 suicidal ideation questions (Categories 1 through 5) on the C-SSRS.
- **Suicidal behavior** - A “yes” answer at any time during study to any 1 of the 5 suicidal behavior questions (Categories 6 through 10) on the C-SSRS.

- **Suicidal ideation or behavior** - A “yes” answer at any time during study to any 1 of the 10 suicidal ideation and behavior questions (Categories 1 through 10) on the C-SSRS.

A listing containing data for each participant with suicidal ideation, suicidal behavior, or nonsuicidal self-injurious behavior during the study by treatment and visit may be provided. Data from all visits are displayed, regardless of a “yes” or “no” answer, for participants with any “yes” answer for suicidal ideation, suicidal behavior, or self-injurious behavior without suicidal intent.

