  - a "yes" answer to any of the suicide-related behaviors (actual attempt, interrupted attempt, aborted attempt, preparatory act or behavior) on the "Suicidal Behavior" portion of the C-SSRS
  - and**
  - the ideation or behavior occurred within the past month
20. Have uncontrolled hypertension (systolic blood pressure above or equal to 160 mmHg and/or diastolic blood pressure above or equal to 100 mmHg)
21. Have any of the following cardiovascular conditions within 3 months prior to Visit 2:
  - acute myocardial infarction
  - cerebrovascular accident (stroke)
  - unstable angina, or
  - hospitalization due to congestive heart failure (CHF)
22. Have NYHA Functional Classification Class IV CHF

23. Have acute or chronic hepatitis, signs and symptoms of any other liver disease other than nonalcoholic fatty liver disease (NAFLD), or any of the following, as determined by the central laboratory during screening:

- alanine aminotransferase (ALT) level  $>3.0X$  upper limit of normal (ULN) for the reference range
- alkaline phosphatase (ALP) level  $>1.5X$  ULN for the reference range, or
- total bilirubin (TBL) level  $>1.2X$  ULN for the reference range (except for cases of known Gilbert's Syndrome)

**Note:** Participants with NAFLD are eligible to participate in this trial if their ALT level is  $\leq 3.0X$  ULN for the reference range.

24. Have a serum calcitonin level (at Visit 1) of

- $\geq 20$  ng/L, if eGFR  $\geq 60$  mL/min/1.73 m^2
- $\geq 35$  ng/L, if eGFR  $< 60$  mL/min/1.73 m^2

25. Have a family or personal history of medullary thyroid carcinoma (MTC) or multiple endocrine neoplasia (MEN) syndrome type 2

26. Have a history of an active or untreated malignancy or are in remission from a clinically significant malignancy (other than basal or squamous cell skin cancer, in situ carcinomas of the cervix, or in situ prostate cancer) for less than 5 years

27. Have any other condition not listed in this section (for example, hypersensitivity or intolerance) that is a contraindication to GLP-1R agonists

28. Have a history of any other condition (such as known drug or alcohol abuse, diagnosed eating disorder, or other psychiatric disorder) that, in the opinion of the investigator, may preclude the participant from following and completing the protocol

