#### **8.2.6. Depression, Suicidal Ideation and Behavior Risk Monitoring**

Patients who have obesity or are overweight are at increased risk for depression (Luppino et al. 2010). Depression can increase the risk for suicidal ideation and behavior. Therefore, study participants will be screened at trial entry and monitored during the study for depression, suicidal ideation and behavior.

Participants should be monitored appropriately and observed closely for suicidal ideation and behavior or any other unusual changes in behavior, especially at the beginning and end of the course of treatment, or at the time of dose changes, either increases or decreases. Consideration should be given to discontinuing intensive lifestyle intervention or the study drug intervention in participants who experience signs of suicidal ideation or behavior, following a risk assessment (Section 7.1).

Baseline and treatment emergent assessment of depression, suicidal ideation and behavior will be monitored during the study using the C-SSRS and PHQ-9 (Section 8.3.2.13).

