4.6. Safety Analyses

Unless specified otherwise, safety assessments for the double-blind period will be based on the SS (Table GPHM.3.1). All data collected between randomization and the end date of study participation will be included, regardless of the adherence to study drug.

Safety outcomes during the intensity lifestyle modification lead-in period will also be summarized for all enrolled participants. Detailed analyses can be found in Appendix 4 (Section 6.4).

The statistical assessment of homogeneity of the distribution of categorical safety responses between tirzepatide and placebo will be conducted using Fisher's exact test, unless specified otherwise.

The mean change from baseline differences among treatments at all scheduled visits will be assessed via an MMRM using REML. Unless specified otherwise, if the safety parameter is assessed at 72 weeks, then the model will include country/pooled country, sex, percentage of body weight reduction at the end of lead-in ($<10\%$ and $\geq 10\%$), treatment group, visit, and treatment-by-visit interaction as fixed effects and baseline value of the safety parameter as a covariate. To model the covariance structure within participants, the unstructured covariance matrix will be used. If this model fails to converge, the covariance structures specified in Section 4.3.2.2 will be tested in order until convergence is met. If the data do not warrant the MMRM model, then an ANCOVA model will be conducted.

For selected parameters, time-to-first-event analysis via the Cox proportional hazards model may be conducted. Participants without the event will be censored at the end of study participation.

For participants experiencing the event, the “time-to-first-event” will be the time (in weeks) from first dose to first occurrence of the event.

Where necessary, the rate of events will be analyzed using a generalized linear mixed model, assuming the number of events follows a negative binomial distribution, with treatment as a fixed effect. The logarithm of days during the active treatment period will be adjusted as an offset, to account for possible unequal treatment duration of follow-up between participants.

Unless otherwise specified, all the analyses listed in this section will be conducted using up to 72 weeks treatment period, plus the safety follow-up (Visit 801), for all randomized participants.

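### The C-SSRS ideation summary never compares post-dose answers with the participant's own pre-dose answers, so recurring Category 1 to 3 ideation is counted like new ideation

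*SAP*

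**What the plan says.** SAP 4.6.5.9.2 sets the window for the single C-SSRS events: "Suicide-related thoughts and behaviors occurring during the entire study period, based on the C-SSRS, will be summarized by treatment group". The ideation composite is a yes "answer at any time during study to any 1 of the 5 suicidal ideation questions (Categories 1 through 5) on the C-SSRS"; the behavior composite and the combined composite are built the same way. The only condition on the denominator is this: "The participants with at least 1 postbaseline C-SSRS assessment are included". The section has no shift table, no worsening outcome and no subset without ideation at baseline. A listing by treatment and visit is optional.

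The subsection just before it, SAP 4.6.5.9.1, treats PHQ-9 differently. Participants are tabulated "within each baseline category (maximum value) versus each postbaseline category (maximum value) by treatment", and three worsening outcomes are compared between treatments, the first being "Any increase in depression category (that is, worsening of depression".

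Protocol 8.2.6 states: "Baseline and treatment emergent assessment of depression, suicidal ideation and behavior will be monitored during the study using the C-SSRS and PHQ-9". Protocol 9.4.4.4.3 leaves the analysis details to the SAP.

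Exclusion criterion 19 (Protocol 5.2) covers a yes to Question 4, a yes to Question 5, or suicidal behavior, on condition that "the ideation or behavior occurred within the past month". It does not name Questions 1 to 3.

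**The concern.** Severe or serious depression and suicidality events are of special interest in this trial, and the C-SSRS is the instrument that asks about ideation directly at almost every contact. The safety question for a drug is whether ideation appears or worsens on treatment. A count of any yes cannot separate that from ideation the participant already had. A participant with a wish to be dead at Visit 2 and again at Visit 14 contributes exactly as one whose first such report comes on study drug. A participant who moves from Category 1 before dosing to Category 4 afterwards is one event in the ideation composite, just like one who stays at Category 1.

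At stake is the sensitivity of the ideation table. The same background added to both arms pulls the risk ratio toward 1 and makes a true increase harder to detect.

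**Working it through.** The documents state no C-SSRS figure, so there is none to reproduce. The check has two parts.

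**Text check**

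- *Pre-dose data exist.* The Schedule of Activities has the C-SSRS at Visits 1, 2, 4, 6, 8 and 10. Protocol 4.1.1.2.3 places the Visit 10 questionnaires before randomization and the first dose.
- *Nothing uses them for comparison.* Table GPHM.4.1 gives baseline rules for adverse events, laboratory tests, vital signs and ECGs, with no C-SSRS row. SAP 4.1 has a default baseline (last nonmissing value at or before randomization), but no C-SSRS outcome refers to it.
- *Category 1 to 3 ideation can be present at entry*, because criterion 19 reaches only Questions 4 and 5 and behavior.
- *The window is not fully clear.* SAP 4.6 says of the double-blind safety analyses: "All data collected between randomization and the end date of study participation will be included, regardless of the adherence to study drug". SAP 4.6.5.9.2 refers to the entire study period. Whether the pre-dose Visit 10 form counts is not stated.

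**Size of the dilution**

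Inputs from the documents: 300 per arm (Protocol 9.2), 2-sided alpha 0.05 (SAP 4.1), Fisher's exact test for categorical safety responses (SAP 4.6).

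Assumed, because the documents give no rates:

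- new-onset ideation p of 1% on placebo and 4% on tirzepatide, among those without recurring ideation;
- b, the share of each arm whose pre-dose ideation recurs after randomization, equal in both arms.

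Formulas:

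- Any-yes risk: q = b + (1 − b)p
- Risk ratio = q(tirzepatide) / q(placebo)
- Risk difference = (1 − b)(4% − 1%)
- New-onset count: (1 − b)p in each arm, so its risk ratio stays at 4.0

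Example, b = 2%: placebo 0.02 + 0.98 × 0.01 = 2.98%; tirzepatide 0.02 + 0.98 × 0.04 = 5.92%; ratio 5.92 / 2.98 = 1.99; difference 2.94 points.

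Power is by exact enumeration of Fisher's test.

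| b | Any yes, placebo vs tirzepatide | Risk ratio | Risk difference (points) | Power, any yes | Power, new-onset count |
|---|---|---|---|---|---|
| 0 | 1.00% vs 4.00% | 4.00 | 3.00 | 58% | 58% |
| 0.5% | 1.50% vs 4.48% | 3.00 | 2.99 | 50% | 58% |
| 1% | 1.99% vs 4.96% | 2.49 | 2.97 | 44% | 57% |
| 2% | 2.98% vs 5.92% | 1.99 | 2.94 | 35% | 57% |
| 5% | 5.95% vs 8.80% | 1.48 | 2.85 | 22% | 55% |
| 8% | 8.92% vs 11.68% | 1.31 | 2.76 | 16% | 53% |

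A second assumed effect, 1% versus 5%, gives the same pattern: the ratio falls from 5.0 to 2.99, 2.32 and 1.64 at b = 1%, 2% and 5%. If 2% have pre-dose ideation but only half of them report it again, the risks are 0.02 × 0.5 + 0.98 × 0.01 = 1.98% and 0.02 × 0.5 + 0.98 × 0.05 = 5.90%, a ratio of 2.98.

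**The case against.** Much can be said for the plan, and most of it narrows the point.

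- *Lead-in ideation.* A reader might infer that ideation reported only before randomization is counted. SAP 4.6 probably rules that out. From Visit 2 the Since Last Visit form is used, so an old yes does not carry forward; the ideation must recur. The recurring case remains, together with the unclear wording of the window.
- *A promised table.* A reader might infer from Protocol 8.2.6 that a specific count was promised and dropped. That section concerns participant monitoring and defines no table. The SAP had a free hand; the point is that it made a weaker choice here than for PHQ-9.
- *Severe categories.* Lifetime attempts, PHQ-9 of 15 or more, and past-month Question 4, Question 5 or behavior are exclusions, and each category is already reported separately by arm. Post-randomization Category 4 to 10 answers will mostly be new. This stands: the behavior composite is little affected.
- *Other routes.* Depression and suicidality adverse events are summarized as treatment-emergent (SAP 4.6.5.9 with 4.6.2.1). This stands too, but they rest on spontaneous reports and do not replace a treatment-emergent summary of the solicited scale.
- *Descriptive table.* The C-SSRS results are to be summarized, whereas the PHQ-9 outcomes are to be compared, so the power of a test is secondary. That is fair; the diluted ratio remains in a descriptive table.
- *Cost of the remedy.* A rule based on the maximum pre-dose category omits on-drug recurrence at the same category. This is correct, and is why the existing tables must stay.

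Nor does Protocol 2.2 support reading the drug as one with a known psychiatric risk: the adverse psychiatric effects mentioned there belong to some earlier centrally acting agents.

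**Conclusion.** The point holds in limited form. SAP 4.6.5.9.2 makes no within-participant comparison, so recurring pre-dose ideation is mixed with new ideation, and worsening inside the composite is not shown. It concerns mainly the ideation composite and Categories 1 to 3.

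It is not a between-arm bias, although the diluted ratio might suggest one. Under the assumptions above, with a 2% background, the excess on tirzepatide is 2.94% × 300 = 8.8 participants against 9.0 without background. What is lost is contrast: the risk ratio falls from 4.0 to between 3.0 and 1.5 for backgrounds of 0.5% to 5%, and power from 58% to between 50% and 22%. These figures rest on assumed rates and on equal recurrence in both arms. In a population screened for psychiatric illness the background may be low, and the loss then smaller. No efficacy conclusion is touched. The change is worth making because the data are already collected and the same SAP uses the better method for PHQ-9.

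**What to change.** In SAP 4.6.5.9.2:

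1. State that C-SSRS counts use only assessments after the first dose, and that the pre-dose Visit 10 form belongs to baseline.
2. Define the C-SSRS baseline from the pre-dose assessments (Visits 1 to 10), stating which recall period of the Visit 1 screening form counts.
3. Add, by arm, a shift table of maximum baseline against maximum postbaseline ideation category (none, 1 to 5).
4. Add, by arm, a count of treatment-emergent ideation, meaning a maximum postbaseline category above the maximum baseline category, with Fisher's exact test as in SAP 4.6.
5. Keep the any-yes and per-category tables, so that recurrence on drug at the same category stays visible.

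The cost is a short SAP revision and one extra table from data already collected. No visit, form or procedure changes.
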